No formal sample size calculation has been performed for the present study, which includes patients who have completed the studies 12709A or 12710A and are eligible for enrolment for this study. Sample size is based on an expected withdrawal of 15-20% of the 1200 patients randomised to the lead-in studies. A maximum of 85% of these lead-in completers are expected to accept to continue into this extension study. This gives approximately 850 patients.

Ethical Rationale for Study and Study Design

In May 2014, WHO's "Health for the world's adolescents" report reveals that "depression is the predominant cause of illness and disability for both boys and girls aged 10 to 19 years" and adds that the "top 3 causes of adolescent deaths globally are road traffic injuries, HIV/AIDS, and suicide. Worldwide, an estimated 1.3 million adolescents died in 2012". The prevalence of Major Depressive Disorder (MDD) is estimated to be approximately 2% in children and 4% to 8% in adolescents.

Only one antidepressant, fluoxetine, is currently approved in Europe for the treatment of MDD in children and adolescents. In the US only fluoxetine is approved for use in children and fluoxetine and escitalopram for use in the adolescent population. Development of a new antidepressant will increase and strengthen the pharmacological treatment options for this patient population. This study is an extension study to Studies 12709A and 12710A and part of the agreed EMA Paediatric Investigational Plan (PIP) and the US Pediatric Written Request (PWR) for vortioxetine with the purpose to investigate the long-term safety and tolerability of vortioxetine in paediatric patients aged 7-17 years. It is the expectation that this study will demonstrate a favourable safety and tolerability profile, and therefore a positive benefit-risk ratio for the use of vortioxetine in the paediatric population.

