5.3 Withdrawal Criteria

A patient must be withdrawn from the study if:

- the patient and/or his or her parent(s)/legal representative(s) withdraw(s) his or her assent/consent (defined as a patient and/or his or her parent(s)/legal representative(s) who explicitly take back his or her assent/consent); section [8.4](#) states how the patient's data will be handled
- the investigator considers it, for safety, lack of efficacy, and/or study compliance reasons, in the best interests of the patient that he or she be withdrawn

- the patient becomes pregnant
- the patient has a serum ALT or AST value >3 times the upper limit of the reference range and a serum total bilirubin value >2 times the upper limit of the reference range
- the patient has a serum ALT or AST value >5 times the upper limit of the reference range that is confirmed by testing <2 weeks later
- the patient has a QTcF interval >500 ms; the decision to withdraw a patient may be postponed until a repeat ECG is taken, if it is taken within 24 hours the patient is lost to follow-up (defined as a patient who fails to comply with scheduled study visits or contact, who has not actively withdrawn from the study, and for whom no alternative contact information is available [this implies that at least two documented attempts have been made to contact the patient])
- the patient and his or her parent(s)/legal representative(s) fails to comply with study procedures
- the patient attempts suicide or is at significant risk of suicide (either in the opinion of the Investigator or defined as a “yes” to suicidal ideation questions 4 or 5 or answering “yes” to suicidal behaviour on the C-SSRS during the study)

Patients who withdraw will not be replaced.

6 Investigational Medicinal Products

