8.4 Withdrawal Visit

Patients who withdraw from the study prior to the Completion Visit will be asked to attend a Withdrawal Visit, if at all possible. The visit must be scheduled as soon as possible after withdrawal.

No new information will be collected from patients who withdraw, except information collected in relation to the scheduled Withdrawal Visit or needed for the follow-up of adverse events (section 10.5).

The reason for withdrawal must be recorded on the *Reason for Withdrawal Form*.

For a patient and/or his or her legal representative (if applicable) who withdraw assent/consent:

- if the patient and/or his or her legal representative (if applicable) withdraw assent/consent during a visit and then agrees to it being the final visit, the investigator will complete the visit as a Withdrawal Visit and all the data collected up to and including this visit will be used
- if the patient and/or his or her legal representative (if applicable) withdraw assent/consent during a telephone conversation, the investigator will ask the patient if he or she will attend a Withdrawal Visit. If the patient:
 - agrees to attend a Withdrawal Visit, all the data collected up to and including this visit will be used
 - refuses to attend a Withdrawal Visit, the investigator should attempt to follow the patient's safety and future treatment; any information collected will only be recorded in the patient's medical record

- if the patient and/or his or her legal representative (if applicable) explicitly request that his or her data collected from the time of withdrawal of assent/consent onwards not be used, this will be respected

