## 10.2 General Efficacy Analysis Methodology

Unless otherwise specified, all the efficacy analyses will be based on the FAS.

All the tables and graphs will be presented for all patients and by lead-in studies and by lead-in treatments, respectively.

Analysis of the endpoints subjected to inferential statistical methods will be presented with 95% CIs.

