## 10.3 Analysis Methodology for the Secondary Endpoints

### 10.3.1 Analysis of the Secondary Endpoints

Absolute values and change from OLEXA in the continuous efficacy variables, except CGI-I, will be summarized descriptively. Absolute values of CGI-I will be summarized.

CDRS-R remission and relapse during treatment period will be summarized descriptively by visit.

For the continuous efficacy variables CDRS-R and CGI-S, change from OLEXA will be analyzed using a restricted maximum likelihood (REML)-based Mixed Model Repeated Measurements (MMRM) approach, using all available observations until completion or withdrawal.

The model will include country, lead-in study interacting with week as factors, and baseline score interacting with week as covariate. An unstructured covariance structure will be used to model the within-patient errors and the Kenward-Roger approximation will be used to estimate denominator degrees of freedom.

For the CDRS-R total score the primary analyses will be also presented by lead-in study by lead-in treatment.

In addition, ANCOVA models will be fitted for CDRS-R and CGI-S, including country and lead-in study as factors and baseline score as a covariate, the analysis will be conducted by visit, based on OC and LOCF.

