### **15 Sample Size Considerations**

No sample size calculation has been performed for the present study, which just includes patients who have completed the studies 12709A or 12710A and are eligible for enrolment for this study.

It is expected that some 15-20% of the 1200 patients randomised to the lead-in studies will drop out and that a maximum of 85% of these “lead-in completers” are expected to accept to continue into this extension study. This gives approximately 850 patients.

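### SAP 10.3.1 supplements the CDRS-R and CGI-S MMRM with OC and LOCF ANCOVAs; LOCF at Week 26 can be biased either way, and none of the three examines worse outcomes after withdrawal

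*SAP*

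**What the plan says.** For change in CDRS-R and CGI-S, SAP 10.3.1 first lists a REML-based MMRM on the data observed up to completion or withdrawal. It then adds ANCOVA models with country, lead-in study and baseline score, where "the analysis will be conducted by visit, based on OC and LOCF". SAP 10.2 adds: "Analysis of the endpoints subjected to inferential statistical methods will be presented with 95% CIs". LOCF is given no rationale and no adjustment to its variance.

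These provisions determine what is missing:

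- Protocol 5.3 requires withdrawal when "the investigator considers it, for safety, lack of efficacy, and/or study compliance reasons, in the best interests of the patient", and also for a suicide attempt or significant suicide risk.
- Protocol 8.4 states "No new information will be collected from patients who withdraw", with exceptions for the Withdrawal Visit itself and the follow-up of adverse events.
- SAP 18.5.1 counts an assessment as valid only if it falls no more than 7 days after the last dose.
- SAP 4 admits a patient to the FAS with a valid OLEXA score and a single valid later CDRS-R. The first scheduled one is at Week 1.
- SAP 18.4 assigns Withdrawal Visit scores to a target day. It also notes that before the second protocol amendment CDRS-R was taken only at Weeks 0, 12 and 26.

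Neither document plans an analysis that varies the assumption about outcomes after withdrawal.

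**The concern.** Each of the three analyses fills the gap after withdrawal in its own way. MMRM assumes that withdrawn patients would have continued like comparable patients who stayed. OC at Week 26 leaves out patients with no score in that window. LOCF freezes them at the last score, which may be 25 weeks old under the current schedule (Week 1 to Week 26), or 14 weeks old for a patient on the earlier schedule last scored at Week 12. The ANCOVA then gives that score the same standing as an observed one.

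The reasons for withdrawal in Protocol 5.3 bear on depressive outcome, so a worse course after leaving is a plausible case. None of the three analyses examines it. With one arm, the resulting bias cannot cancel in a between-group contrast. Three similar Week 26 estimates could be read as evidence that the result is robust to missing data, which they would not be.

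**Working it through.** **1. The plan's own figure.** Inputs are in the Protocol Synopsis and 17.12: "Sample size is based on an expected withdrawal of 15-20% of the 1200 patients randomised to the lead-in studies" and "A maximum of 85% of these lead-in completers are expected to accept to continue into this extension study".

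N = 1200 x (1 - dropout) x 0.85

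- 15% dropout: 1200 x 0.85 x 0.85 = 867
- 17.5% dropout: 1200 x 0.825 x 0.85 = 841.5
- 20% dropout: 1200 x 0.80 x 0.85 = 816

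SAP 15 says "This gives approximately 850 patients", which lies within 816-867. It is the only planning figure available: "No sample size calculation has been performed for the present study". The documents give no CDRS-R SD, no withdrawal rate for the extension and no target precision. Every other input below is an assumption.

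**2. Nominal precision of the LOCF ANCOVA at Week 26.** LOCF uses nearly everyone, so n is about 850. With SD 12 (assumed), SE = 12/sqrt(850) = 0.41 and the 95% half-width is 1.96 x 0.41 = 0.81. With SD 10 and 15 the half-widths are 0.67 and 1.01.

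**3. Shift if scores worsen after the last observation.** For LOCF, shift = d x b, where d is the share withdrawn and b the mean number of points lost after the last score.

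| Share withdrawn | 5 points lost | 10 points lost |
|---|---|---|
| 15% | 0.75 | 1.50 |
| 17.5% | 0.875 | 1.75 |
| 30% | 1.50 | 3.00 |

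Against a half-width of 0.81 this is about 0.9 to 3.7 half-widths. The 3.00 needs both upper assumptions together.

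**4. Width, by formula.** If the last score explains a share R2 of Week 26 variance and a share w is missing, the SE should be larger by 1/sqrt(1 - w(1 - R2)).

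- w = 0.15, R2 = 0.5: 1/sqrt(0.925) = 1.04, so the LOCF SE is about 4% too small.
- w = 0.30, R2 = 0.3: 1/sqrt(0.79) = 1.125, so it is about 11% too small.

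**5. Width and bias, by simulation.** The set-up was 850 patients, SD 12, scores at Weeks 0, 1, 2, 4, 8, 12, 18 and 26, and 600 replicates. The 24 scenarios crossed withdrawal of about 10, 17.5 or 30%, a correlation parameter of 0.5 or 0.7, a mean that was flat or improved by 8 points, and withdrawal that was random or likelier with worse scores. The comparator was a missing-at-random maximum-likelihood estimate.

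- The ratio of the LOCF model SE to the comparator's SE ran from 0.83 to 1.04 and was below 1 in 22 of 24 scenarios. The Monte Carlo error of each comparator SE is about 1/sqrt(2 x 600) = 3%, so ratios close to 1 cannot be told from 1.
- With a flat mean and random withdrawal, the LOCF CI covered the Week 26 mean 0.94-0.96 of the time. In all other scenarios coverage was 0.00-0.83.
- Those failures come mainly from bias, and here the bias ran against the drug. For a true change of -8 with 17.5% random withdrawal and correlation parameter 0.5, LOCF gave -7.25. With score-linked withdrawal it gave -5.86.

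So LOCF understates improvement when patients would have gone on improving (step 5) and overstates it when they lose ground after leaving (step 3). Bias is the larger fault, and narrowness the smaller one.

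**The case against.** The strongest reply is that LOCF carries little weight here. MMRM comes first and the ANCOVAs are additional. That stands. A reader might infer that the effectiveness result rests on LOCF, and the SAP does not support that.

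Second, a patient leaving for lack of efficacy should have CDRS-R and CGI-S at the Withdrawal Visit, and SAP 18.4 windows those scores in, so the poor score reaches MMRM and LOCF. This stands for patients who attend. It also means that OC is not strictly limited to patients who stayed, since a late Withdrawal Visit could be placed at a scheduled week; the rules are in a Data Handling Plan that is not among these documents. Neither fact says anything about the weeks that follow.

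Third, if LOCF is read as change to the last on-treatment score, nothing is missing and its CI is not too narrow. That is fair, but the endpoint in SAP 3.2 is change to Week 26 and the ANCOVA is run by visit, so the output would be read as a Week 26 result unless labelled otherwise.

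Fourth, dropout is visible: SAP 6.2 gives withdrawals by reason and Kaplan-Meier time to withdrawal, and remission and relapse are summarised by visit. Visible is not the same as modelled, and SAP 17 removed the time-to-relapse and time-to-loss-of-remission analyses.

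Two stronger readings also fail. LOCF does not always overstate benefit; the direction depends on the course after withdrawal, which the documents cannot tell us. Nor is its CI always too narrow: in 2 of 24 scenarios the SE was not smaller.

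**Conclusion.** The point holds as a weakness in the supportive efficacy analysis. The LOCF ANCOVA is a poor estimate of the Week 26 mean, with bias of unknown sign and an SE usually too small, by a few percent up to about 17%. More importantly, agreement among MMRM, OC and LOCF would not show that the Week 26 estimate withstands worse outcomes after withdrawal.

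The illustrative overstatement of 0.75-3.0 CDRS-R points, against a half-width of about 0.8, rests on assumed withdrawal of 15-30%, a loss of 5-10 points after the last score and SD 12. Only n = 850 comes from the documents. The figures show what such losses would do, not what will happen.

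The primary objective is safety, and efficacy is secondary with no stated hypothesis test. The change is worth making, but nothing in the primary evaluation depends on it.

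**What to change.** In SAP 10.3.1, replace the Week 26 LOCF ANCOVA for CDRS-R and CGI-S with an ANCOVA on multiply imputed data:

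1. Impute under missing at random, consistently with the MMRM. Patients on the earlier CDRS-R schedule have planned gaps, which should be imputed without penalty.
2. Repeat with fixed, prespecified worsening penalties added to the Week 26 imputations of withdrawn patients, for example 2.5, 5 and 10 CDRS-R points. Use a scaled equivalent for CGI-S, such as the same multiples of its SD. At 15-30% withdrawal these move the CDRS-R mean by 0.375-0.75, 0.75-1.5 and 1.5-3.0 points.
3. Combine by Rubin's rules and report the set as a range of Week 26 estimates with CIs.

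Two common variants should be avoided. Imputing to OLEXA as if benefit were lost does not work: OLEXA is the lead-in Completion Visit, 12 weeks after Baseline A (SAP 3.2 and 18.1). It therefore keeps any lead-in gain and can be kinder than LOCF to a patient who has worsened since. A tipping rule cannot be applied either, because no efficacy threshold is stated.

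Keep OC as descriptive. If LOCF is retained, label it change to last on-treatment score and not a Week 26 result.

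The cost is SAP wording and modest programming, with no new data. The supportive estimate may be less favourable and its CI slightly wider.

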## 11 Palatability and Acceptability

Palatability and acceptability assessments were performed in 10 countries only.

Each assessment contains 7 questions, 4 on palatability and 3 on acceptability. Palatability assessment includes taste, mouthfeel, aftertaste and smell, based on 5-points hedonic scales. Acceptability assessment includes acceptability of the taste, ease of use and willingness to take the drops every day, based on 3-points scales.

Palatability and acceptability item scores will be summarized using descriptive statistics.

The oral drops were considered acceptable if the mean hedonic scores were  $\leq 3$  for each aspect of palatability (taste, aftertaste, smell and mouthfeel), *and*  $<60\%$  of participants responded “no” to each of the 3 questions regarding acceptability.

### Panel 3 Palatability and acceptability

Endpoint	Description	Type
Palatability and acceptability	Absolute value of palatability	1
	Absolute value of acceptability item scores	1

1 = continuous; 2 = binary

## 12 Safety

### 12.1 Adverse Events

#### 12.1.1 General Methodology for Adverse Events

Unless otherwise specified, tables, graphs, and listings will be based on the APTS.

All the tables will be presented for all patients and by lead-in study and by lead-in treatment, respectively, unless otherwise specified.

Tables by preferred term and tables by system organ class (SOC) and preferred term will be sorted in descending order by the overall percentage of patients.

Unless otherwise specified, the summaries of adverse events will include the total number and percentage of patients with an adverse event, and the total number of events. For sex-specific preferred terms, the denominator in the % calculations will be the number of patients of that sex. Sex-specific preferred terms will be marked in the summaries.

In summaries of adverse events presented by intensity, the maximum intensity of the adverse event will be used for patients who have more than one intensity of that event. Adverse events for which information on intensity is missing will be classified as severe.

Listings of adverse events will be sorted by site, lead-in study, lead-in treatment, patient number, and adverse event start date, and include preferred term, investigator term, adverse

event start date, days since first dose of IMP, duration of the adverse event, date of death, action taken, causality, intensity, seriousness, and outcome. For adverse events that change in intensity, each intensity will be included.

### **12.1.2 Handling of Adverse Events**

#### **12.1.2.1 Adverse Events Changing in Intensity or Seriousness**

In ADaM data, changes in intensity are included as additional records (rows) to the originally reported adverse events.

If an adverse event changes from non-serious to serious, in addition to the originally reported adverse event start date, the start date for the seriousness is reported. In ADaM data, adverse events that change from non-serious to serious will be included as two records, one with seriousness non-serious and one with seriousness serious.

#### **12.1.2.2 Coding of Adverse Events**

Adverse events will be coded using MedDRA, Version 22 or later.

#### **12.1.2.3 Classification of Adverse Events**

Adverse events will be classified according to the time of onset of the adverse events:

- *Lead-in adverse event* – an adverse event starts before visit 1 in 12712A and ongoing from (= with start date in) lead-in study 12709A or 12710A
- *treatment-emergent adverse event* – an adverse event that starts or increases in intensity/or seriousness at or after visit 1 of study 12712A

An adverse event is considered causally related to the use of the IMP when the causality assessment by the investigator is *probable* or *possible*.

#### **12.1.2.4 Assigning Adverse Event Records to an Analysis Phase**

All records for an adverse event will be assigned to an analysis phase. The analysis phase will determine how an adverse event record is reported, and an adverse event may be reported in more than one analysis phase insofar as it worsens.

For further details, see [Data Handling Plan](#).

### **12.1.3 Summary of All Adverse Events**

All adverse events will be listed, including a flag for TEAE.

An overview of the PYE, numbers, and percentages of patients with TEAE, serious adverse events (SAEs), or adverse events leading to withdraw, and of patients who died will be

provided for APTS. For TEAE, SAEs, and adverse events leading to withdrawal, the total number of events will be included.

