# 2 Study Design

This is an interventional, multi-national, multi-site, open-label, flexible-dose, long-term extension study in child and adolescent patients with MDD who completed one of the double-blind, placebo-controlled, active-reference studies 12709A and 12710A.

The Baseline Visit, hereafter referred to as OLEXA, of this extension study, will be Visit 12 (Completion Visit) of lead-in Study 12709A or 12710A, see section 18.1.

The dosage of vortioxetine will be initiated at 5 mg/day for the first 2 days prior to receiving 10 mg/day. The target dose is 10 mg/day; however, the investigator has the possibility to adjust the dose in case of unsatisfactory response up to 20 mg or in case of dose-limiting adverse events. The dose can be up or down titrated with 5 mg/day. The patient should receive the same dose for 2 days before being up-titrated to a new dose. Changes in dosing may occur at any site visit during the treatment course at the investigator's discretion but the maximum dose may not exceed 20 mg/day.

[figure not shown]
For subset of patients participating in the palatability assessment (patients enrolled in Bulgaria, Estonia, Germany, Latvia, Mexico, Poland, Russia, Serbia, Ukraine, and Colombia), palatability and acceptability of vortioxetine oral drops will be assessed after intake of a single dose (5-20 mg) corresponding to the patient's current vortioxetine dose (instead of their vortioxetine tablet on that day). The assessment can be done at any visit to the clinic from Week 4 to Week 18 (i.e., at Visits 5, 7, 9, or 11).

The treatment period is 26 weeks. The total study duration per patient from OLEXA to the end of follow-up will be approximately 30 weeks.

If possible, patients who withdraw are to be seen for a withdrawal visit as soon as possible and they will be contacted for a safety follow-up visit 4 weeks after withdrawal.

The study design is presented in [Panel 1](#).

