## 9 Exposure and Compliance

Exposure (days) to IMP will be calculated as:

- Date of last dose of IMP – Date of first dose of IMP in study 12712A + 1

Exposure to IMP will be summarized for all patients and by lead-in study and by lead-in treatment using descriptive statistics, and, will include the patient years of exposure (PYE). PYE will be calculated as the sum of the number of days of exposure to IMP for each patient, divided by 365.25 days.

In addition, exposure to IMP will be categorized in intervals (1 – 14 days, 15 – 35 days, 36 – 70 days, 71 – 105 days, 106 – 140 days, 141 – 182 days and >182 – days) and summarized by lead-in study and by lead-in treatment. Missing values of exposure will not be imputed.

Non-compliant days are days on which no IMP has been taken, less than the full dose of IMP has been taken, or more than the full dose of IMP has been taken.

Compliance (%) with IMP will be calculated as:

- $(\text{date of Completion/Withdrawal Visit} - \text{date of Visit 1} - \text{number of days of non-compliance}) / (\text{date of Completion/Withdrawal Visit} - \text{date of Visit 1}) \times 100\%$

where the number of non-compliant days is defined as the sum of all non-compliant days in the treatment period.

Compliance with IMP will be categorized as “≤80% compliant” or “>80% compliant”. The number and percentage of patients in each category will be summarized by lead-in study and lead-in treatment, respectively, by visit interval and for the entire study.

The mean and modal dose of IMP will be calculated for each patient and summarised (mean, median, and lower and upper quartiles for the mean and counts for the modal dose). IMP dose level at the completion or withdrawal of the study will be summarized. Number and percentage of patients who reached highest and lowest dose level will be summarised. In addition, number and percentage of patients with each dose level will be summarised by visit.

Number of patients who exposed to oral drops will be summarized.

Exposure and compliance will be summarized based on the APTS.

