#### **12.1.5 Summary of Treatment-emergent Adverse Events**

The following summaries will be provided for the APTS:

- TEAE by SOC and preferred term
- TEAE by preferred term
- TEAE with an incidence > 2% and 5% by preferred term
- Causally related TEAE by SOC and preferred term
- TEAE by intensity (*mild/moderate/severe*), and preferred term
- Causally related TEAE by intensity and preferred term

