#### **12.1.9 Adverse Events Related to Tolerability**

Incidence and prevalence rates in every four-week interval will be presented for nausea based on the APTS for events with complete start and stop dates.

Incidence will be defined as the number of patients with a new event in the specified time interval. The denominator in each interval will be the number of patients without the event at

the start of the interval plus the number of patients with an ongoing event at the start of the interval for which the event stops before the end of the interval.

Prevalence will be defined as the number of patients with the event at the start of the interval or who have the event during the interval. The denominator will be the number of patients at the start of the interval.

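### Apart from nausea, the SAP reports adverse events as crude percentages and puts patient-years of exposure into no rate, so the primary safety figures depend on how long patients stayed on treatment

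*SAP*

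**What the plan says.** Safety is the primary objective, and adverse events head the list of primary endpoint components (SAP 3.1). SAP 12.1.1 fixes the general measure: "the summaries of adverse events will include the total number and percentage of patients with an adverse event, and the total number of events". The denominator is the all-patients-treated set (APTS), which a patient enters with a single dose (SAP 4).

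SAP 9 defines exposure in time: "PYE will be calculated as the sum of the number of days of exposure to IMP for each patient, divided by 365.25 days". SAP 12.1.3 places that total in the overview, described as "An overview of the PYE, numbers, and percentages of patients with TEAE", and adds: "For TEAE, SAEs, and adverse events leading to withdrawal, the total number of events will be included". Nothing in either document divides events, or patients with events, by PYE, and no time-to-event estimate of adverse event risk is planned. SAP 12.1.5 includes a frequency-limited table, "TEAE with an incidence > 2% and 5% by preferred term", alongside unrestricted tables by preferred term.

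On layout, SAP 12.1.1 states: "All the tables will be presented for all patients and by lead-in study and by lead-in treatment, respectively, unless otherwise specified". On follow-up, SAP 2 states: "The treatment period is 26 weeks".

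The one time-specific adverse event analysis is in SAP 12.1.9: "Incidence and prevalence rates in every four-week interval will be presented for nausea based on the APTS for events with complete start and stop dates".

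**The concern.** In a crude percentage, a patient who stopped after a few days counts in the denominator exactly as one treated for 26 weeks. For an event that can occur at any time, the percentage therefore falls as withdrawal rises, even when the underlying hazard is unchanged. A reader who takes the figure as the risk of half a year of treatment will take it too low.

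The same mechanism acts on the columns by lead-in treatment. The lead-in studies had placebo and active-reference arms, so some patients meet vortioxetine for the first time here. Only lead-in completers enter, and a moderate or severe ongoing event related to lead-in medication excludes a patient if the investigator considers it a potential safety risk (Protocol 5.2, inclusion criterion 7 and exclusion criterion 3). Former vortioxetine patients are thus selected for tolerating the drug and the others are not. Different withdrawal patterns are plausible, although the documents do not state or predict them.

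A reader can repair only part of this. Event totals stand beside PYE for three overview categories, so events per PYE can be formed there. That cannot be done by preferred term from the adverse event tables as specified, and it cannot be done for first events, because time at risk up to the first event is not derived.

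**Working it through.** **The plan's own figures.** No adverse event risk, rate, PYE total or extension withdrawal rate is stated. The only related figure that can be recomputed is enrolment (Protocol 17.12, SAP 15): 1200 × 0.85 × 0.85 = 867 and 1200 × 0.80 × 0.85 = 816, so approximately 850 lies inside the range. With 850 patients, the maximum PYE is 850 × 182 / 365.25 = 424. The 15-20% dropout in those sections concerns the lead-in studies and does not give a rate for the extension.

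**Assumptions.** R is the 26-week risk under full exposure. W is the 26-week withdrawal for reasons unrelated to the event. Both are assumed, with W taken from 10% to 40%. Hazards are constant and withdrawal is independent of the event.

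**Formula.** With λ = −ln(1 − R) and μ = −ln(1 − W):

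crude percentage = λ/(λ + μ) × [1 − exp(−(λ + μ))]

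Example for R = 10%, W = 20%: λ = 0.1054, μ = 0.2231, exp(−(λ + μ)) = 0.90 × 0.80 = 0.72. Crude = 0.1054/0.3285 × 0.28 = 9.0%.

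Mean exposure, ignoring the event, is 26 × W/μ weeks.

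| W | Crude % for R = 10% | Relative shortfall | Mean exposure (weeks) | PYE for 850 patients |
|---|---|---|---|---|
| 10% | 9.5 | 5% | 24.7 | 402 |
| 15% | 9.2 | 8% | 24.0 | 391 |
| 20% | 9.0 | 10% | 23.3 | 380 |
| 30% | 8.4 | 16% | 21.9 | 356 |
| 40% | 7.9 | 21% | 20.4 | 332 |

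The relative shortfall is nearly the same for R between 2% and 20%.

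**Sensitivity to timing.**
- All event hazard in weeks 0-2, withdrawal constant: a true 10% shows as 9.96% (W = 10%) to 9.81% (W = 40%), a shortfall of 0.4-2%.
- Event hazard constant, all withdrawal in weeks 0-4: a true 10% shows as 9.1% (W = 10%) to 6.3% (W = 40%), a shortfall of 9-37%.

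**Two lead-in groups with the same true 10% risk.**

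| Withdrawal in the two groups | Crude percentages | Difference (points) |
|---|---|---|
| 15% v 20% | 9.2 v 9.0 | 0.3 |
| 15% v 30% | 9.2 v 8.4 | 0.8 |
| 10% v 40% | 9.5 v 7.9 | 1.6 |

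**What a first-event rate would show.** Patient-years at risk per patient are (182/365.25) × [1 − exp(−(λ + μ))]/(λ + μ). At W = 10% this is 0.4983 × 0.19/0.2107 = 0.449, and 0.0950/0.449 = 21.1 per 100 patient-years. At W = 40% it is 0.4983 × 0.46/0.6162 = 0.372, and 0.0787/0.372 = 21.1. Under these assumptions the rate does not move with withdrawal.

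**Whether numerator and denominator match.** Treatment-emergent events have a start but no stated end (SAP 12.1.2.3), and new serious events are collected at the safety follow-up (Protocol 8.5), while exposure ends at the last dose (SAP 9). Patients with a missing dose start or stop date get no exposure (SAP 18.5.1) but stay in the APTS counts. The Data Handling Plan may close the event window; the SAP does not. Even the rate a reader can form from the overview may therefore use mismatched windows.

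**The case against.** The strongest reply is that exposure is not hidden and the crude percentage is not wrong. Every patient is scheduled for the same 26 weeks, so the percentage validly describes how often events were observed when withdrawal is a competing event. It is low only as a risk under full exposure. Exposure and PYE (SAP 9) and Kaplan-Meier time to withdrawal (SAP 6.2) are all shown by lead-in treatment, and nausea has its own interval analysis. All of this stands, and it limits the point to a missing complement.

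Three stronger readings are tempting and are not supported.

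- A reader might infer that the plan compares lead-in groups as though their exposure were equal. No test, contrast or confidence interval between lead-in groups is planned for adverse events. The columns are descriptive, and the primary objective is addressed by an overall clinical evaluation (Protocol 17.10.1).
- A reader might infer that the group with more withdrawal always looks safer. That follows only if withdrawal is unrelated to the event. A patient who stops because of an adverse event has had the event and counts in the numerator.
- A reader might infer that events slip out of sight because a crude figure falls below the 5% display limit. SAP 12.1.5 also plans unrestricted tables by preferred term, so no event is lost.

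It is also fair to say that a Kaplan-Meier estimate for events leading to withdrawal, with other withdrawals censored, exceeds the proportion who actually withdraw for adverse events. It is useful only if labelled for what it estimates.

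**Conclusion.** The point holds as a cheap improvement to the reporting of the primary safety endpoint. Outside nausea, the planned adverse event figures are crude percentages and counts, and PYE enters no rate. Read as full-exposure 26-week risks, the percentages are low by about 5-21% in relative terms for 10-40% withdrawal with constant hazards. The shortfall is at most about 2% for events confined to the first two weeks, and larger if withdrawal is concentrated early. The effect on the lead-in treatment columns ranges from 0.3 to 1.6 percentage points at a true 10% risk over the pairs examined.

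These sizes rest on assumed withdrawal rates, constant hazards except in the two timing cases, and withdrawal independent of the event. Unequal exposure between lead-in groups is plausible from the design but is not documented.

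**What to change.** Keep all planned crude percentages. In SAP 12.1.3, 12.1.7, 12.1.8 and 12.1.10, and in the > 2% table of 12.1.5, add the number of patients with a first event per 100 patient-years at risk. End time at risk at the first event or at the end of the on-treatment window, whichever comes first. State that window in the SAP, apply it to both events and exposure, and say how patients with missing dose dates are handled. Show the rate for all patients and by lead-in treatment.

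For serious adverse events and adverse events leading to withdrawal, add a Week 26 Kaplan-Meier estimate, labelled as the risk under continued treatment with other withdrawals censored. Print the crude percentage beside it as the observed proportion when other withdrawal is a competing event.

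Cost: SAP wording and larger tables. The dates needed are already collected, but SAP 9 derives only total exposure, so time at risk to first event must be newly derived. A rate per patient-year suits early-clustered events poorly because it spreads them over the whole period; for those, the crude percentage remains the better summary.
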